#### 5.3.3.9 Composite normalization

The definition of composite normalization is the condition of the value  $\leq$  ULN of any type of cortisol. For any given time point a responder in this composite will be defined a patients with mUFC  $\leq$  ULN, or salivary cortisol  $\leq$  ULN (if mUFC is missing), or serum cortisol  $\leq$  ULN (if mUFC and salivary cortisol are missing).

The number and proportion of participant achieving composite normalization at 4, 8, 12, 24, 36 and every 12 weeks thereafter will be summarized descriptively along with associated 95% CI.

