#### 3.6.2 Secondary (Supportive) Endpoints

The secondary endpoints are:

- a) Proportion of patients with mUFC  $\leq$  ULN at weeks 24, 36 and every 12 weeks until the earlier of loss to follow-up, death, or the end of the retrospective follow-up period or treatment.
- b) Change from baseline for biochemical variables to Week 4, 8, 12, 18, 24, 36, and to every 12 weeks until the earlier of loss to follow-up, death, or the end of the retrospective follow-up period or treatment.
- c) Actual and percent Change in BMI, ECG, blood pressure, metabolic, biochemical, and hormone levels from baseline for clinical outcomes to Week 4, 8, 12, 18, 24, 36, and to every 12 weeks until the earlier of loss to follow-up, death, or the end of the retrospective follow-up period or treatment discontinuation
- d) Change from initial dose.
- e) Proportion of participants who experienced TEAE and AESI

Project Document Version No.: 4.0; Document Effective Date: 30 October 2023

CONFIDENTIAL

- f) Change from baseline of measures of cortisol levels (mUFC, salivary cortisol and morning serum cortisol expressed as x-fold the ULN) to Week 4, 8, 12, 18, 24, 36, and to every 12 weeks until the earlier of loss to follow-up, death, or the end of the retrospective follow-up period or treatment.
- g) Partial responders (defined as patients with a ≥50% reduction from baseline, but still >ULN) for measures of cortisol levels (mUFC, salivary cortisol and morning serum and a combination of the 3 measures) to Week 4, 8, 12, 18, 24, 36, and to every 12 weeks until the earlier of loss to follow-up, death, or the end of the retrospective follow-up period or treatment discontinuation.
- h) Complete or partial responders: Proportion of participants with normalization of cortisol levels or a partial response: for cortisol levels (mUFC, salivary cortisol and morning serum and combination of the 3 measures) to Week 4, 8, 12, 18, 24, 36, and to every 12 weeks until the earlier of loss to follow-up, death, or the end of the retrospective follow-up period or treatment discontinuation.
- Composite of normalization cortisol measures at week 12: Patients with W12 mUFC ≤ ULN, or W 12 salivary cortisol ≤ ULN (if w12 mUFC is missing), or W 12 serum cortisol ≤ ULN (if W12 mUFC and salivary cortisol are missing)

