# 5.3.3.7 Complete or partial responder

The number and proportion of complete or partial responders at Week 4, 8, 12, 18, 24, 36, and to every 12 weeks thereafter will be summarized descriptively along with associated 95% CI.

This will be reported for mUFC, salivary cortisol and morning serum cortisol as well as the combination of the 3 measures (any of the measures and reported as "Cortisol").

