#### 5.3.3.10 Time to normalization

Time to normalization is the interval between start of osilodrostat administration and time of normalization of cortisol levels.

Project Document Version No.: 4.0; Document Effective Date: 30 October 2023

CONFIDENTIAL

RECORDATI AG, Rare Diseases Branch LCI699-RECAG-NI-0596

Statistical Analysis Plan

The participants not reaching the normalization will be censored at the date of the last available cortisol measure.

In the case of the composite analysis the baseline would be the closest measure to the start of osilodrostat among the different cortisol assessments (mUFC, salivary and serum) and the time of normalization is the first occurring among the cortisol measures. Censored dates will be the date of the last available cortisol measure. In case of multiple measures at a timepoint the the definition of composite normalization will be applied.

This will be reported for mUFC, salivary cortisol and morning serum cortisol as well as the combination of the 3 measures (any of the measures and reported as "Cortisol").

The number and proportion of events and censored values will be presented together with median time, (95% CI), quartiles, minimum and maximum and Kaplan-Meier curves will be produced for analysis.

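### The SAP gives two incompatible rules for the composite cortisol response: any measure in range, or an mUFC-first hierarchy. The looser rule can only raise the secondary rates.

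*SAP*

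**What the plan says.** **Composite normalization (SAP 5.3.3.9).** The section begins "The definition of composite normalization is the condition of the value" at or below "ULN of any type of cortisol". The sentence after it ranks the measures: mUFC decides; salivary cortisol counts only when mUFC is absent; serum counts only "if mUFC and salivary cortisol are missing".

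**Week 12 composite (SAP 3.6.2, last item).** Only the hierarchy appears: mUFC, "or W 12 salivary cortisol ≤ ULN (if w12 mUFC is missing"), then serum if both are missing.

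**Combined Cortisol rows (SAP 5.3.3.6, 5.3.3.7, 5.3.3.8 and 5.3.3.10).** Each reports the three measures separately and then a "combination of the 3 measures (any of the measures and reported as" Cortisol). No ranking is given.

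**Time to normalization (SAP 5.3.3.10).** For the composite, "the time of normalization is the first occurring among the cortisol measures". Where several measures fall at one timepoint, "the definition of composite normalization will be applied", which points back to 5.3.3.9.

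**Elsewhere.** SAP 3.6.3 (on-treatment analyses) and 5.10 (subgroups) use the words combination or composite without naming a rule.

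**The concern.** The two rules disagree whenever the highest-ranked measure available is above ULN and a lower-ranked one is in range. The important case is a patient whose mUFC has failed but whose morning serum or salivary value is normal. That patient is a responder under *any* and a non-responder under the hierarchy. mUFC is the primary variable (protocol 8.3.1), so *any* would let a secondary assay overturn the primary measure. It would also favour patients who had more assays done.

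The responder categories are affected too. SAP 5.3.3.6 requires a partial responder to be still above ULN. If each measure can qualify a patient on its own, someone with mUFC halved but above ULN and serum in range is both a partial responder (on mUFC) and a complete responder (on serum) in the combined row.

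These are secondary and exploratory effectiveness results in a study meant to support an sNDA (SAP 1). The composite is not in protocol Table 1, and SAP 5.13 mentions added analyses without itemising them. Two competent programmers could produce different tables from this text.

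**Working it through.** The documents state no composite rate, so there is no figure to reproduce. The check is of direction first, then of size.

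**Direction.** Take one timepoint and one denominator. A hierarchy responder has the deciding measure at or below ULN, so at least one measure is in range and the patient is also an *any* responder. The converse fails for discordant patients. Hence the *any* rate is never below the hierarchy rate and exceeds it whenever such patients exist. By the same argument, the first normalization under *any* is never later than under the hierarchy.

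**Inputs from the documents.** About 100 patients (SAP 5.12); exact Clopper-Pearson intervals (SAP 5.2); assessments recorded only if available (SAP Table 1, footnote b).

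**Inputs assumed.** The documents give no salivary or serum normalization rate, no correlation between measures and no availability. I assume a 50% rate for each measure and a latent Gaussian correlation ρ, equal for all pairs, from 0 to 0.8.

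**Complete data, all three measures present.** The hierarchy gives the mUFC rate, 50%. For 50% rates, P(no measure in range) = 1/8 + (3/4π)·arcsin ρ, and *any* = 1 − that probability.

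- ρ = 0: 1 − 0.125 = 87.5%
- ρ = 0.5: 1 − (0.125 + 0.125) = 75.0%
- ρ = 0.8: 1 − (0.125 + 0.2214) = 65.4%

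At ρ = 1 the two rules coincide at 50%.

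**Half the patients with all three measures, half with one.** A patient with a single measure is classified identically under both rules, so *any* = 0.5 × (complete-data value) + 0.5 × 50%.

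- ρ = 0: 0.5 × 87.5 + 25 = 68.8%
- ρ = 0.5: 0.5 × 75.0 + 25 = 62.5%
- ρ = 0.8: 0.5 × 65.4 + 25 = 57.7%

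**If only a quarter have all three and the rest have one.** The same weighting gives 59.4%, 56.3% and 53.8%.

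**Scale.** 50/100 has a 95% interval of 39.8% to 60.2%, about 10 points either side. The gap between rules is 15 to 38 points with complete data, 8 to 19 points with half, and 4 to 9 points with a quarter. It can exceed the sampling uncertainty but need not.

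**A different assumed rate.** The nearest mUFC rate in the documents is 6/9 = 66.7%, from the Japanese phase II study of non-CD CS (protocol 6). Using it for all three measures with complete data, the hierarchy gives 66.7% and *any* gives 96.3% at ρ = 0 (1 − (1/3)³), 87.9% at 0.5 and 80.2% at 0.8.

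**The case against.** The best defence is that the operative rule is clear. The second sentence of 5.3.3.9 is a complete definition for any timepoint, 3.6.2 repeats it, and the opening sentence can pass as a loose summary. Section 5.3.3.10 sends same-timepoint measures back to that definition, so its first-occurring clause bites mainly on measures taken at different times. The combination rows may be a different output from the composite, since 3.6.2 lists them separately. The words *any of the measures* need not mean a logical OR: in 5.3.3.8 they follow a criterion based on at least 50% of measures, where pooling is the more natural reading. The separate mUFC, salivary and serum rows would also expose a divergent combined row.

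Much of this stands. It limits the claim about 5.3.3.10, and it means one cannot assert that every Cortisol row uses an OR. It does not remove the conflict. The opening sentence of 5.3.3.9 is still there, and it is part of the definition to which 5.3.3.10 refers. The unranked wording appears in four other sections. The SAP never says that combination and composite differ, and 3.6.3 applies its week 12 composite item to a combination of the three measures.

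A reader might infer that the same patients would yield about 50% under one rule and 70% to 90% under the other. The documents do not support that as a result. Rates of 50% mUFC, 30% salivary and 70% serum give 1 − 0.5 × 0.7 × 0.3 = 89.5% under independence, but the 70% floor is simply the assumed serum rate, and every patient must have all three assays. With 50% for each measure, 70% is reached only if ρ is about 0.67 or lower.

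**Conclusion.** The conflict is in the text and should be resolved. The direction is certain if *any* is programmed as an OR: the combined rates can only rise, because a failed mUFC can be overridden. The size is illustrative only. On an assumed 50% per measure, it is 50% against about 65% to 88% with complete data, and against about 58% to 69% if half the patients have one measure, for latent correlation 0.8 down to 0. Fewer multiply-assayed patients or stronger correlation shrink it further.

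It would be wrong to carry the point over to the primary endpoint. That uses mUFC alone (SAP 3.6.1 and 5.3.2) and is unaffected. This is a defect in secondary and exploratory effectiveness outputs that should be corrected in the SAP.

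**What to change.** 1. Delete the opening *any type of cortisol* sentence of 5.3.3.9 and keep the hierarchy.
2. Apply the 3.6.2 hierarchy to the composite and to the combined Cortisol outputs for partial response, complete or partial response, and time to normalization (5.3.3.6, 5.3.3.7, 5.3.3.10). mUFC then decides whenever it is available at that timepoint, and complete and partial response are mutually exclusive.
3. For the 50%-of-measures output in 5.3.3.8 and 3.6.3, do not impose the hierarchy by default, because it could discard data. State separately how the measures are pooled, and settle the threshold, which is at least 50% in 5.3.3.8 and more than 50% in 3.6.3.
4. Name the rule wherever 3.6.3 and 5.10 use composite or combination.
5. If an *any* result is kept, label it supplementary and report the number of patients with discordant measures beside it.

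The cost is SAP wording and one derived variable, with no new data collection. The downside for the sponsor is that the combined rates may be less favourable.

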#### 5.3.3.10 Time to normalization

Time to normalization is the interval between start of osilodrostat administration and time of normalization of cortisol levels.

Project Document Version No.: 4.0; Document Effective Date: 30 October 2023

CONFIDENTIAL

RECORDATI AG, Rare Diseases Branch LCI699-RECAG-NI-0596

Statistical Analysis Plan

The participants not reaching the normalization will be censored at the date of the last available cortisol measure.

In the case of the composite analysis the baseline would be the closest measure to the start of osilodrostat among the different cortisol assessments (mUFC, salivary and serum) and the time of normalization is the first occurring among the cortisol measures. Censored dates will be the date of the last available cortisol measure. In case of multiple measures at a timepoint the the definition of composite normalization will be applied.

This will be reported for mUFC, salivary cortisol and morning serum cortisol as well as the combination of the 3 measures (any of the measures and reported as "Cortisol").

The number and proportion of events and censored values will be presented together with median time, (95% CI), quartiles, minimum and maximum and Kaplan-Meier curves will be produced for analysis.

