#### Type of interventions

The participants will be classified according to the interventions they received:

- 1) *Tx naïve*: All patients who were treated with Osilodrostat as monotherapy that were not taking any medical therapy for Cushing's syndrome prior to the start of Osilodrostat (limited to somatostatin analogues, dopaminergic medications, and steroidogenesis inhibitors)
- Switch group: All patients who were treated with Osilodrostat as monotherapy but were taking any medical therapy for Cushing's syndrome and discontinued these prior to the start of Osilodrostat.
- 3) **Combination Tx**: All patients treated with both Osilodrostat and any medical therapy for Cushing's syndrome.

Project Document Version No.: 4.0; Document Effective Date: 30 October 2023

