# 3.6.3 Exploratory endpoint(s)

The exploratory effectiveness endpoint is:

- a) Proportion of participants with normal late night salivary cortisol at Week 4, 8, 12, 18, 24, 36, and at every 12 weeks until the earlier of loss to follow-up, death, or the end of the retrospective follow-up period or treatment discontinuation
- b) On-treatment analysis of cortisol levels
  - a. Normalization of cortisol measures at Week 4, 8, 12, 18, 24, 36, and at every 12 weeks until the earlier of loss to follow-up, death, or the end of the retrospective follow-up period or treatment discontinuation (mUFC, salivary cortisol and serum cortisol and a combination of the 3 measures). Participants with normal values at baseline would not enter in this analisis.
  - b. Composite of normalization of week 12 cortisol measures: For patients taking Osilodrostat on week 12 (mUFC, salivary cortisol and morning serum and a combination of the 3 measures).
  - c. Normalization to the last on treatment cortisol measures (mUFC, salivary cortisol and morning serum and a combination of the 3 measures).
  - d. Patients with normalization of the majority of cortisol measures: Defined as patients on Osilodrostat treatment that have multiple measures of cortisol levels over time and have >50% of these measures ≤ ULN (mUFC, salivary cortisol and morning serum and a combination of the 3 measures).
  - e. Change from baseline of measures cortisol level: Defined as the change from baseline in measures of cortisol levels including only patients receiving Osilodrostat the time-point (expressed by the unit and bx nfold ULN) for mUFC, salivary cortisol and morning serum and a combination of the 3 measures.
  - f. Complete or partial responders: The proportion of patients with normalization of cortisol levels or a ≥50% reduction from baseline for patients receiving Osilodrostat at week 4, 8, 12, 18, 24, 36, and at every 12 weeks until the earlier of loss to follow-up, death, or the end of the retrospective follow-up period or treatment discontinuation (mUFC, salivary cortisol and morning serum and a combination of the 3 measures).
  - g. Waterfall plot figures of change in measures of cortisol level from baseline to last on treatment expressed as n-fold ULN (mUFC, salivary cortisol and morning serum and a combination of the 3 measures) grouped by duration of exposure to osilodrostat (0 to 4 weeks, 5 to 8 weeks, 9 to 12 weeks, 13 to 24 weeks, >24 weeks).

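### Time to normalization (SAP 5.3.3.10) does not remove participants already ≤ULN at baseline, so part of each Kaplan-Meier curve, and possibly the median, reflects pre-treatment status

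*SAP*

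**What the plan says.** SAP 5.3.3.10 defines the variable: "Time to normalization is the interval between start of osilodrostat administration and time of normalization of cortisol levels". On censoring it says: "The participants not reaching the normalization will be censored at the date of the last available cortisol measure". The analysis is run for mUFC, salivary cortisol, morning serum cortisol and the three combined. The outputs are event and censoring counts together with "median time, (95% CI), quartiles, minimum and maximum and Kaplan-Meier curves will be produced for analysis".

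For the combined curve, the baseline is the cortisol measure closest to the start of osilodrostat, and "the time of normalization is the first occurring among the cortisol measures". A further sentence limits this: "In case of multiple measures at a timepoint the the definition of composite normalization will be applied". SAP 5.3.3.9 defines composite normalization as "the condition of the value" being at or below ULN. It uses mUFC first, salivary cortisol only if mUFC is missing, and serum cortisol only if both are missing.

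SAP 3.6.3 b.a, the on-treatment normalization by visit, carries a rule that 5.3.3.10 lacks: "Participants with normal values at baseline would not enter in this analisis".

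The inclusion criteria (SAP 3.1, Protocol 8.2.1) require a documented diagnosis of CS but no cortisol level above ULN at first dose. SAP 3.5 includes a Combination group and a Switch group. The latter, with the first osilodrostat dose as the reference point, is described as "All patients who were treated with Osilodrostat as monotherapy but were taking any medical therapy for Cushing's syndrome and discontinued these prior to the start".

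**The concern.** Normalization is defined as a state (a value ≤ULN), not as a move from above ULN to ≤ULN. The rule in 5.3.3.10 uses the first-dose date, the dates of later cortisol values, and whether each is ≤ULN. It never says what the baseline value does. A participant who starts ≤ULN and stays there has an event at the first visit, usually Week 4, with nothing having changed.

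Such participants are foreseeable. Eligibility does not require raised cortisol at first dose. Some participants come from, or remain on, other therapy for CS. The curve is drawn for each of three analytes, and nothing requires a participant to be raised on all three.

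The study has no comparator and is meant to support a supplemental application. A reader will take the median as the speed of response. Baseline-normal participants raise the early part of the curve and shorten the median even when the drug works.

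**Working it through.** The documents give no event count, median or power for this analysis, so there is no planned figure to reproduce. They also give no baseline cortisol distribution. Every size below rests on a stated assumption.

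**1. Effect on the median when the drug works**

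Let *g* be the share ≤ULN at baseline who are still ≤ULN at Week 4, and *F(t)* the cumulative share normalized among baseline-high participants. The reported curve is then *g* + (1 − *g*)·*F(t)*. Assume *F* = 0.25, 0.40 and 0.50 at Weeks 4, 8 and 12, a true median of Week 12. Censoring is ignored.

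| *g* | Week 4 | Week 8 | Week 12 | Median |
|---|---|---|---|---|
| 0 | 0.25 | 0.40 | 0.50 | Week 12 |
| 0.10 | 0.10 + 0.90×0.25 = 0.325 | 0.10 + 0.90×0.40 = 0.46 | 0.10 + 0.90×0.50 = 0.55 | Week 12 |
| 0.20 | 0.20 + 0.80×0.25 = 0.40 | 0.20 + 0.80×0.40 = 0.52 | – | Week 8 |
| 0.30 | 0.30 + 0.70×0.25 = 0.475 | 0.30 + 0.70×0.40 = 0.58 | – | Week 8 |
| 0.50 | 0.50 + 0.50×0.25 = 0.625 | – | – | Week 4 |

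Setting the formula to 0.5 gives the switch points under this *F*. The median moves to Week 8 once 0.6*g* ≥ 0.10, that is *g* ≥ 1/6, and to Week 4 once 0.75*g* ≥ 0.25, that is *g* ≥ 1/3.

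**2. What the curve shows with no drug effect, single analyte**

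If baseline-normal participants are the only source of events, the curve is flat at *g*, and a median exists only if *g* ≥ 50%.

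Values also cross ULN by chance. A simulation of stable log-normal cortisol used the SAP visit grid, exponential follow-up with mean 60 weeks capped at 156, between-patient log SD 0.8 and within-patient log SD 0.5, all assumed:

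| Typical level | ≤ULN at baseline | Week 36, as written | Week 36, baseline-high only | Median, as written → baseline-high only |
|---|---|---|---|---|
| 1.5×ULN | 33% | 60% | 43% | Week 12 → Week 84 |
| 2×ULN | 23% | 47% | 34% | Week 60 → not reached |
| 3×ULN | 12% | 29% | 22% | not reached → not reached |
| 5×ULN | 4% | 13% | 10% | not reached → not reached |

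With more noise (within-patient log SD 0.7), 3×ULN reaches a median at Week 96 as written. At 5×ULN no median was reached at any variability tried.

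**3. Combined curve with the hierarchy applied**

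Assume 11%, 19% and 50% of single values ≤ULN for mUFC, salivary and serum cortisol, no drug effect, and serum always available. If mUFC is available with probability *a* and salivary cortisol with probability *b*, the share counted at Week 4 is

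*a*×0.11 + (1 − *a*)·*b*×0.19 + (1 − *a*)(1 − *b*)×0.50.

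- *a* = 1: 11%.
- *a* = 0.8, *b* = 0.5: 0.088 + 0.019 + 0.050 = 16%.
- *a* = 0.6, *b* = 0.4: 0.066 + 0.030 + 0.120 = 22%.
- *a* = 0.5, *b* = 0.3: 0.055 + 0.029 + 0.175 = 26%.

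Simulating the same settings over five visits to Week 24 gives 23%, 39%, 53% and 60%. This used medians of 3, 2.2 and 1.0×ULN, between-patient log SDs 0.8/0.8/0.4, within-patient log SDs 0.4/0.4/0.25, and correlation 0.6 between patient means. These totals include chance crossings by baseline-high participants. The hierarchy holds the figure down when mUFC is present, and serum brings it back up when mUFC and salivary values are missing.

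**The case against.** **Silence is not an instruction.** The section names a baseline for the combined curve and speaks of participants not reaching normalization, so the authors may have meant baseline-normal participants to be left out. That is fair: the SAP does not state that they stay in. But no exclusion is written, the baseline is given no function, and a programmer following the text would count them. Since 3.6.3 b.a states the exclusion for its own analysis, its absence here needs resolving either way.

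**Any normal value counts.** A reader might infer that one normal serum value ends the clock in the combined curve even beside a raised mUFC. It does not when both belong to the same timepoint, because the composite hierarchy then applies.

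**The curve says nothing about the drug.** A reader might infer that the analysis cannot tell an active drug from an inert one, or that it is the SAP's only evidence on speed of response. Neither is supported. Change from baseline, partial and complete response, and normalization are all planned at Weeks 4, 8 and 12, and 3.6.3 b.a excludes baseline-normal participants. The study is descriptive, and time to normalization is not in the SAP 3.6 endpoint list.

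**The filter is partial.** Baseline-high participants can still cross ULN by chance, so 22-43% are counted by Week 36 in the 1.5-3×ULN rows above even after exclusion. This stands. The filter removes the part due to starting status, not the part due to measurement noise.

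**Conclusion.** The concern holds in a limited form. As written, 5.3.3.10 turns participants already ≤ULN at baseline into events at their first post-dose visit if they remain ≤ULN. Part of each curve is then unrelated to drug effect, and the median may be.

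Whether the median moves depends on the baseline-normal share, which the documents do not state. Under the assumed response curve it moves one visit earlier from about 17% baseline-normal and two visits earlier from about 33%. With no drug effect, a median appears only at typical levels near ULN or with high variability. The documents therefore do not support a claim that most of the curve, or the median in general, would arise without the drug.

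This is more than a missing detail, because the text as it stands can change a reported result, and the SAP already handles the same problem in a related analysis. It should be corrected, but it does not touch the primary endpoint.

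**What to change.** Amend SAP 5.3.3.10 as follows.

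1. For each analyte, restrict the Kaplan-Meier analysis to participants whose baseline value of that analyte is >ULN. Report beside the curve the number excluded as already ≤ULN and, separately, the number with no baseline value.
2. For the combined curve, include only participants whose composite baseline is >ULN. Keep the SAP's mUFC, salivary, serum hierarchy for the event.
3. If the all-participant curve is wanted, keep it as a supportive output labelled *time to first value ≤ULN, including participants ≤ULN at baseline*.

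The filter also needs a stated baseline window. SAP 5.2 gives 2 weeks for all variables, while footnote f of SAP Table 1 allows 1 month for mUFC.

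The change costs a few sentences and one baseline filter in the programs, with no new data. The price is fewer participants in each curve, wider intervals and a longer, less favourable median.
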